1.3 Schedule of Activities (SoA)

TABLE 1: SCHEDULE OF ACTIVITIES: INTERVENTIONAL SUBJECTS

Study Procedure:	Screening ≤14 days prior to Day 0	Day 0 : Begin TMZ Treatment	Week 4 (-3/+7 days) and every 4 weeks until treatment stop	Week 8 (±7 days) and every 8 weeks only until treatment stop	Progression	After Treatment Stop (Week 4 (+/- 7 days) from end of treatment)	Survival follow-up
Informed Consent	X						
Medical History, Demographics	X						
Medication History	X						
MGMT methylation status	X						
Tumor Tissue Sample ⁹	X				X		
MRI of the brain ¹	X			X	X		
Physical Exam	X		X		X	X	
Neurological status, KPS	X		X		X	X	
CBC w/diff	X ¹⁰		X		X	X	
Pregnancy test (urine or serum)	X ¹⁰						
Biochemistry Panel ⁶	X ¹⁰		X		X	X	
Record Steroid Dose	X		X		X		
Quality of Life Questionnaires ²	X			X	X		
RANO	X			X	X		
Temozolomide Cycle		X ⁷	X ⁸				

Study Procedure:	Screening ≤14 days prior to Day 0	Day 0 : Begin TMZ Treatment	Week 4 (-3/+7 days) and every 4 weeks until treatment stop	Week 8 (±7 days) and every 8 weeks only until treatment stop	Progression	After Treatment Stop (Week 4 (+/- 7 days) from end of treatment)	Survival follow-up
Optune Therapy ⁴		X	X		X		
Optune Compliance ⁴			X				
Adverse Events		X	X	X	X	X	
Concomitant Medications		X	X	X	X	X	
Telephone Interview							X ⁵
DICOM Images shipped for electric fields mapping ¹¹		X			X		X

1) Screening MRI should be done within 21 days of study treatment start. MRI of the brain will be performed routinely at baseline and again every 8 weeks +/- 7 days until treatment termination or second progression, whichever is first. An MRI of the head will be obtained within 21 days in the event of clinical signs of progression. After the post-treatment follow up visit and the patient has not progressed by treatment termination, patient will have contrast-enhanced brain MRI every 3 +/- 1 months for 12 months, then every 6 +/- 2 months for 24 months, then yearly +/- 1 month thereafter or until disease progression, whichever comes first. All MRI scans should be performed with and without contrast and include the scalp.
							

2) Quality of Life will be measured using the EORTC QLQ-C30/BN20 and MMSE every 8 weeks +/- 7 days for the first 2 years then every 3 months thereafter.
							

3) Screening visit should occur within 14 days of adjuvant temozolomide start, with the exception of MRI which can be within 21 days (3 weeks) of adjuvant temozolomide start.
							

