3 OBJECTIVES AND ENDPOINTS

TABLE 2: OBJECTIVES & ENDPOINTS

OBJECTIVES	ENDPOINTS	JUSTIFICATION FOR ENDPOINTS
Primary		
To determine whether TTFIELDS combined with adjuvant temozolomide increases OS in patients with newly diagnosed Grade II and III astrocytoma with TERT promoter mutation only compared to historical and contemporaneous controls.	OS measured in days from Study Day 0 until death. If the study ends and the participant is still living, OS will be measured in days from Study Day 0.	OS remains the primary concern within this patient population. Intent to Treat analysis will be used to determine if this objective is met.
Secondary		

 To determine whether the combination of TTFIELDS and adjuvant temozolomide is safe in the newly diagnosed high-risk Grade II and III astrocytoma. To determine whether TTFIELDS combined with adjuvant temozolomide increases PFS in patients with newly diagnosed Grade II and III astrocytoma with TERT promoter mutation only compared to historical and contemporaneous controls. To evaluate QOL using KPS, EORTC QLQ-C30/BN20, and MMSE in patients treated with TTFIELDS combined with adjuvant temozolomide compared to 	
 PFS measured in days from Day 0 to progression Safety measured by incidence and severity of Adverse Events and Toxicities. Quality of life measured by KPS, EORTC QLQ-C30/BN20, and MMSE Correlation between % Compliance with TTFIELDS and OS 	Safety, Efficacy, and Quality of Life measures for a more complete view of the effects of the study treatment(s).

historical and contemporaneous controls.		
Tertiary/Exploratory		

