9 CONTROL COHORT

This trial will include a control cohort that includes both historical and contemporaneous control patients. A minimum of 90 and a maximum of 100 patients will be enrolled in the control cohort. This is a non-interventional control group (data collection only). All patients in the control cohort will be enrolled at the same participating institutions. Risks associated with participation of the control cohort are minimal.

Historical controls will be gathered via chart review of patients completing chemo/RT after 1/1/2016 and before 5/20/2019; 5/20/2019 is the initial date of IRB approval for the coordinating center and first opened study site. Control patients completing chemo/RT after 5/20/2019 will be enrolled as contemporaneous controls.

Control subjects (contemporaneous or historical) will be enrolled via informed consent if consent is practicable. An IRB waiver of consent will be requested for historical control patients who may be deceased, no longer being followed or lost to follow-up.

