9.2 Control Cohort Inclusion Criteria

In order to be eligible to enroll in the control cohort, an individual must meet all of the following criteria:

- A. Willing and able to provide written informed consent or eligible for inclusion under an IRB-approved waiver of consent
- B. Male or female, 18 years or older

- C. Histologic confirmation of WHO Grade II or III astrocytoma
 - a. mixed oligoastrocytomas are permitted
- D. Mutational identity determined by CLIA-certified sequencing including:
 - a. IDH1/2 wildtype (i.e. lack of detectable mutations on the sequencing report, variants of unknown significance or non-synonymous single nucleotide polymorphisms deviating from wild-type sequence do not apply)
- AND
- b. TERT promoter mutation(s)
- E. Karnofsky performance status $\geq 70\%$
- F. Maximal safe resection
 - a. biopsy alone is allowed
- G. Completed standard chemoradiation and concurrent temozolomide and adjuvant temozolomide.
 - a. Patients with a tumor that was biopsied or resected in the past followed by observation only without definitive chemoradiation and/or chemotherapy given will be eligible, as long as: repeat maximal surgical resection (biopsy only allowed) has been performed, definitive temozolomide/RT treatment meets the criteria above, and adjuvant temozolomide treatment was given (or planned for the contemporaneous cohort)
- H. Candidate for adjuvant high dose temozolomide per investigator's clinical judgement (for the contemporaneous cohort)
- I. No evidence of early disease progression per RANO criteria upon completion of Chemo/RT and beginning adjuvant temozolomide

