9.5 Control Cohort Limited Data Collection

Data collected for the historical and contemporaneous control group will be distinct from data collected for interventional patients in this study, as described below. Data for control patients is designed to be collected exclusively from chart review.

All control cohort documentation should be uploaded into the eCRF within 45 days of collection. Data extracted from the medical record shall be defined as collected on the day of extraction.

1. Informed Consent or waiver
2. Demographics

3. Pathology
4. Date of and extent of operation (GTR, partial, or biopsy)
5. Summary of Concurrent Chemo/RT

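### Contemporaneous controls who consent after Day 0 bring guaranteed survival time into the OS comparison, and the planned log-rank test does not remove it

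*Combined protocol and SAP*

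**What the plan says.** **Who is a contemporaneous control.** Section 9 decides by the date chemoradiation ended: "Control patients completing chemo/RT after 5/20/2019 will be enrolled as contemporaneous controls". The historical window runs from 1 January 2016 to that date. Section 10.1 expects between 80 historical plus 10 contemporaneous and 60 plus 30.

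**How controls enter.** Section 9: "Control subjects (contemporaneous or historical) will be enrolled via informed consent if consent is practicable". The only waiver request described is the one for historical controls: "An IRB waiver of consent will be requested for historical control patients who may be deceased, no longer being followed or lost to follow-up". Section 9.2, criterion A, is broader: "Willing and able to provide written informed consent or eligible for inclusion under an IRB-approved waiver of consent". Section 9.5 lists "Informed Consent or waiver" as the first data item for both control types together. Section 11.2.2.1 asks for a signed and dated consent form and names no waiver alternative.

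**Time origin and test.** Section 3, Table 2: "OS measured in days from Study Day 0 until death". The Section 1.3 schedule labels that day "Day 0 : Begin TMZ Treatment". It is the interventional schedule; no Day 0 is defined for controls. Section 10.2.1 plans a log-rank test and mentions no delayed entry. Section 10.2.1 names only the historical arm, but Sections 10.1 and 10.2 pool both control types into one arm, and that pooled comparison is taken here.

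**Timing of consent.** No section says when a contemporaneous control must consent relative to Day 0.

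**The concern.** If a patient can join the control arm only by consenting in person, and does so some time after the OS clock has started, the interval up to consent is time in which that patient could not have been recorded as dead. Similar patients who died in that interval never enter. An ordinary log-rank test from Day 0 nevertheless counts the interval as time at risk, so control survival looks better than it is.

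The treated arm has no matching feature, because its patients consent before Day 0. The effect is to shrink an apparent TTFields benefit. In a trial of a rare subgroup, with power only moderately above 80% at the smaller effect sizes, the risk is missing a real benefit.

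**Working it through.** **1. Reproduce the planned power.** Inputs from Sections 10.1 and 10.2: control median 22 months, gain 6 months, 90 treated and 90 controls, one-sided alpha 0.05, Weibull shape k = 2.0 or 1.8. Under proportional hazards HR = (22/28)^k, which is 0.617 for k = 2.0 and 0.648 for k = 1.8. With follow-up uniform on 24 to 60 months the expected events D are 146.0 and 142.3. Power = Φ(√(D/4) × |ln HR| − 1.645):

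- k = 2.0: Φ(6.04 × 0.482 − 1.645) = 0.898; Table 10 gives 0.895 for 60+30.
- k = 1.8: Φ(5.96 × 0.434 − 1.645) = 0.827; Table 10 gives 0.823.

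The plan's figures are reproduced.

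**2. What lag do the dates support?** Section 11.4 shows the control cohort being added in the version of 16 December 2019. From 20 May 2019 that is 210 days. The interventional schedule puts adjuvant temozolomide 28 to 42 days after radiotherapy; the same gap is assumed for controls. So 210 − 42 = 168 days to 210 − 28 = 182 days, about 5.5 to 6.0 months. The earliest contemporaneous controls were already that far past Day 0 when the version was dated, and further if approval or site activation came later. No document gives the lag for anyone else.

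**3. What does a lag L do to one patient?** With S(t) = exp(−ln 2 × (t/22)^k), the share dead before L is 1 − S(L), and the median given survival to L is 22 × (1 + (L/22)^k)^(1/k).

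| L (months) | Dead before L, k=2.0 | Median given alive at L, k=2.0 | Dead before L, k=1.8 | Median given alive at L, k=1.8 |
|---|---|---|---|---|
| 3 | 1.3% | 22.2 | 1.9% | 22.3 |
| 6 | 5.0% | 22.8 | 6.5% | 23.2 |
| 12 | 18.6% | 25.1 | 20.8% | 25.8 |

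The accelerating hazard keeps the effect small at short lags.

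**4. What does it do to the trial?** Log-rank simulation (8,000 replicates per scenario), true 6-month gain, follow-up uniform on 24 to 60 months. Every contemporaneous control is drawn as alive at a consent time spread uniformly over the stated range.

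| Contemporaneous controls | k | Consent lag (months) | Planned test | With delayed entry |
|---|---|---|---|---|
| 30 | 2.0 | 0-6 | 0.889 | about 0.895 |
| 30 | 2.0 | 0-12 | 0.870 | about 0.895 |
| 30 | 2.0 | 0-18 | 0.824 | about 0.895 |
| 30 | 1.8 | 0-6 | 0.812 | 0.825 |
| 30 | 1.8 | 0-12 | 0.777 | 0.827 |
| 10 | 2.0 | 0-6 | 0.899 | about 0.90 |
| 10 | 2.0 | 0-12 | 0.894 | about 0.90 |
| 10 | 2.0 | 0-18 | 0.874 | about 0.90 |

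Repeat runs agree to about one point: for 30 controls at k = 2.0 they give 0.88, 0.86 to 0.87, and 0.82 to 0.83 in the three lag ranges.

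**5. Direction.** Under no treatment effect, with 30 contemporaneous controls and k = 2.0, the simulated one-sided type I error is 0.055 with no lag, 0.044 with lags of 0-6 months, and 0.016 if all 30 consent at 12 months. It falls; it does not rise.

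**The case against.** The strongest reply is that contemporaneous controls are mostly not late consenters. Section 5.1, criterion O, sends a patient who declines the device to this cohort while adjuvant temozolomide alone is still the plan. Sections 10.1 and 10.3 describe these patients as trial-eligible people who declined Optune by preference. In Section 9.2, criterion H requires candidacy for adjuvant temozolomide, and item G.a allows it to be only planned. All of this points to consent around the device decision, near or before Day 0, where there is no guaranteed time. That stands, and it limits the point to those who consent later.

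A reader might infer more in four places; the documents do not support it.

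- *That every contemporaneous control must survive to a late consent, so a third of the control arm is biased.* This needs 30 such controls (30/90), all consenting late, with no waiver for any of them.
- *That they are found by chart review.* The sentence in Section 9.5, "Data for control patients is designed to be collected exclusively from chart review", concerns how data are obtained. Section 9 ties identification by chart review to historical controls.
- *That the waiver is firmly closed to them.* Section 9.2 A and the first item of Section 9.5 are not limited to historical controls. The scope is ambiguous, though no wider request is described.
- *That lags of a year are built in.* The main text of criterion G, read literally, puts enrolment after adjuvant temozolomide is finished, and with 6 to 12 cycles in the treated arm that would mean roughly 6 to 12 months. Criterion H and item G.a point the other way, so this remains a possibility and not a documented lag.

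What the reply does not remove: near-Day-0 consent is allowed but not required, and the dates make it impossible for the earliest patients to have consented as controls by Day 0.

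**Conclusion.** The concern holds for contemporaneous controls who consent after Day 0, and only for them. At the lag the dates support, the effect is small: about 1 point of power with 30 such controls at k = 2.0, and 1 to 2 points at k = 1.8. If consent is spread over 0-12 months, the loss with 30 controls is about 3 points (k = 2.0) to 5 points (k = 1.8), and the plan's own alternative shape then gives about 0.78 against the stated 80%. With 10 such controls at k = 2.0 the loss is about 1 point or less up to 12 months.

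The bias works against the device, so it gives no ground for expecting a false claim of benefit.

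These sizes assume that Section 9 governs the waiver, that Day 0 for controls is the start of adjuvant temozolomide, and that all contemporaneous controls follow the stated lag range. The lag distribution is not in the documents. The correction is worth making because it is cheap and recovers the loss, not because the loss is known to be large.

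**What to change.** 1. Define Day 0 for controls as day 1 of adjuvant temozolomide cycle 1, and record each control's consent date as an analysis variable.
2. In the OS log-rank or Cox analysis, let consented contemporaneous controls enter the risk set at the later of Day 0 and consent (left truncation). Patients consented by Day 0 are unaffected. This assumes that, among survivors, the time of consent is unrelated to prognosis.
3. Alternatively, extend the waiver request to deceased contemporaneous controls, so that all eligible patients enter from Day 0. This avoids that assumption but needs IRB agreement.
4. Reconcile the waiver scope across Sections 9, 9.2 A, 9.5 and 11.2.2.1, and state when contemporaneous controls are expected to consent.

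The cost of delayed entry is a little pre-consent person-time and one line of analysis code. The consent date is already on the signed form that Section 11.2.2.1 requires. In the simulations, delayed entry kept power within about a point of its no-lag value.

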9.1 Control Cohort Rationale

Identification of a homogeneous historical cohort for comparing the investigational device data to historical data is of critical importance to this study's design and scientific rigor. This historical and contemporaneous cohort will include patients completing radiation and chemotherapy treatment no earlier than January 1, 2016, when chemotherapy became the care standard in these tumor subtypes [16].

9.2 Control Cohort Inclusion Criteria

In order to be eligible to enroll in the control cohort, an individual must meet all of the following criteria:

- A. Willing and able to provide written informed consent or eligible for inclusion under an IRB-approved waiver of consent
- B. Male or female, 18 years or older

- C. Histologic confirmation of WHO Grade II or III astrocytoma
 - a. mixed oligoastrocytomas are permitted
- D. Mutational identity determined by CLIA-certified sequencing including:
 - a. IDH1/2 wildtype (i.e. lack of detectable mutations on the sequencing report, variants of unknown significance or non-synonymous single nucleotide polymorphisms deviating from wild-type sequence do not apply)
- AND
- b. TERT promoter mutation(s)
- E. Karnofsky performance status $\geq 70\%$
- F. Maximal safe resection
 - a. biopsy alone is allowed
- G. Completed standard chemoradiation and concurrent temozolomide and adjuvant temozolomide.
 - a. Patients with a tumor that was biopsied or resected in the past followed by observation only without definitive chemoradiation and/or chemotherapy given will be eligible, as long as: repeat maximal surgical resection (biopsy only allowed) has been performed, definitive temozolomide/RT treatment meets the criteria above, and adjuvant temozolomide treatment was given (or planned for the contemporaneous cohort)
- H. Candidate for adjuvant high dose temozolomide per investigator's clinical judgement (for the contemporaneous cohort)
- I. No evidence of early disease progression per RANO criteria upon completion of Chemo/RT and beginning adjuvant temozolomide

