5 STUDY POPULATION

5.1 Inclusion Criteria

In order to be eligible to participate in this study, an individual must meet all of the following criteria:

- A. Willing and able to provide written informed consent
- B. Stated willingness to comply with all study procedures and availability for the duration of the study
- C. Male or female, 18 years or older
- D. Life expectancy of at least 3 months
- E. Histologic confirmation of WHO Grade II or III astrocytoma
 - a. mixed oligoastrocytomas are permitted
- F. Mutational identity determined by CLIA-certified sequencing including:
 - a. IDH1/2 wildtype (i.e. lack of detectable mutations on the sequencing report, variants of unknown significance or non-synonymous single nucleotide polymorphisms deviating from wild-type sequence do not apply)
AND
 - b. TERT promoter mutation(s)
- G. Karnofsky performance status $\geq 70\%$
- H. Maximal safe resection
 - a. biopsy alone is allowed
- I. Completed standard chemoradiation with total RT dose of at least 40 Gy and concurrent temozolomide (75mg/m² daily dose with 80% prescribed dose completed)
 - a. Patients with a tumor that was biopsied or resected in the past followed by observation only without definitive chemoradiation and/or chemotherapy given will be eligible, as long as: repeat maximal surgical resection (biopsy only allowed) has been performed, definitive temozolomide/RT treatment meets the criteria above, and adjuvant temozolomide treatment is planned
- J. Candidate for adjuvant high dose temozolomide per investigator's clinical judgement
- K. Adjuvant Temozolomide start date at least 4 weeks, but not more than 6 weeks, from the later of last dose of concomitant temozolomide or radiotherapy
- L. No evidence of early disease progression per RANO criteria at the time of enrollment
- M. Women of childbearing potential (WOCBP) must be using a highly effective method of contraception to

avoid pregnancy throughout the study and for at least 24 weeks after the last dose of study drug to minimize the risk of pregnancy.

- a. Prior to study enrollment, women of childbearing potential must be advised of the importance of avoiding pregnancy during trial participation and the potential risk factors for an unintentional pregnancy.
 - b. Refer to section 10.2.1 for guidance on highly effective contraceptive methods acceptable in this study.

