5.2 Exclusion Criteria

An individual who meets any of the following criteria will be excluded from participation in this study:

- A. Prior treatment with anti-angiogenic agents including bevacizumab.
- B. Prior treatment with TTFIELDS.
- C. Progressive disease (according to RANO criteria) after temozolomide/RT.
- D. Actively participating in another clinical treatment trial intended to treat the underlying astrocytoma.
- E. Females who are pregnant or breastfeeding.
- F. Significant co-morbidities at baseline (within 2 weeks prior to adjuvant temozolomide start) which would prevent adjuvant temozolomide treatment:
 - a. Thrombocytopenia (platelet count $< 100 \times 10^3/\mu\text{L}$)
 - b. Neutropenia (absolute neutrophil count $< 1.5 \times 10^3/\mu\text{L}$)
 - c. CTC grade 4 non-hematological toxicity (except for alopecia, nausea, vomiting)
 - d. Significant liver function impairment - AST or ALT > 5 times the upper limit of normal
 - e. Total bilirubin > 2 times upper limit of normal
 - f. Significant renal impairment (GFR ≤ 30 ml/min)
- G. Implanted pacemaker, programmable shunts, defibrillator, deep brain stimulator, other implanted electronic devices in the brain, or documented clinically significant arrhythmias.
- H. A skull defect such as missing bone with no replacement
- I. Bullet fragments embedded the skull
- J. Tumors located in the brain stem and/or the cerebellum.
- K. History of hypersensitivity reaction to temozolomide, Dacarbazine (DTIC) or hydrogel.

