6.1.2.4 Temozolomide Dose Reduction or Discontinuation

Dose reductions during the adjuvant phase should be applied according to Tables 7 and 8 below. Cycle 1 Day 1 should not start until the ANC is above 1.5 x 10⁹/L (1,500/μL) and the platelet count exceeds 100 x 10⁹/L (100,000/μL). If unable to start within the Cycle 1 start window, the patient will be considered a screen fail.

The next cycle of temozolomide should not be started until the ANC and platelet count exceed these levels. Dose reductions during the next cycle should be based on the lowest blood counts and worst non-hematologic toxicity during the previous cycle. Dose reductions or discontinuations during the adjuvant phase should be applied according to Tables 7 and 8. Routine blood monitoring should be conducted in accordance with local site procedures.

TABLE 7. TEMOZOLOMIDE DOSE LEVELS FOR ADJUVANT TREATMENT

Dose Level	Dose (mg/m ² /day)	Remarks
-1	100	Reduction for prior toxicity
0	150	Dose during Cycle 1
1	200	Dose during Cycles 2-12 in absence of toxicity

TABLE 8. TEMOZOLOMIDE DOSE REDUCTION OR DISCONTINUATION DURING ADJUVANT TREATMENT

Toxicity	Reduce temozolomide by 1 Dose Level ^a	Discontinue temozolomide
Absolute Neutrophil Count	<1.0 x 10 ⁹ /L	See footnote b
Platelet Count	<50 x 10 ⁹ /L	See footnote b
CTC Non-hematological Toxicity (except for alopecia, nausea, vomiting)	CTC Grade 3	See footnote b

^a: temozolomide dose levels are listed in table 7.

^b: temozolomide is to be discontinued if dose reduction to <100 mg/m² is required or if the same Grade 3 non-hematological toxicity (except for alopecia, nausea, vomiting) recurs after dose reduction.

CTC = Common Toxicity Criteria.

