9.3 Control Cohort Exclusion Criteria

At time of starting adjuvant (first-line) therapy:

- L. Prior treatment with anti-angiogenic agents including bevacizumab.
- M. Progressive disease (according to RANO criteria) after temozolomide/RT, at time of starting adjuvant therapy.
- N. Actively participating in another clinical treatment trial intended to treat the underlying astrocytoma at start of adjuvant Temozolomide treatment.

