10 STATISTICAL CONSIDERATIONS

10.1 Statistical Hypotheses

- Primary Efficacy Endpoint: overall survival (OS)

Control arm: the control arm will consist of both historical and contemporaneous control patients. Historical controls will consist of TERT mutation-only astrocytoma patients treated and followed by the participating sites between January 1, 2016 and May 20, 2019. As described above, these patients will have received standard treatment and would have met first tier inclusion/exclusion criteria for the study. Data for these patients will be collected via chart review. Contemporaneous controls will also consist of patients who qualify for the trial and receive standard treatment but decide not to proceed with the Optune experimental treatment because of personal preference. This personal preference must be non-medical in nature. Based on clinical experience, most commonly this non-medical patient personal preference preventing Optune use will be unwillingness to shave his/her head and/or unwillingness to wear a visible medical device on his/her head most of the day.

- N = 90 patients total in an expected mixture ranging between 80 historical controls and 10 contemporaneous controls to 60 historical controls and 30 contemporaneous controls.
- Assumed median survival = 22 months (based on Figure 3A in Eckel-Passow et al [12])
- Follow-up = up to 60 months for the historical controls, up to 60 months for the contemporaneous controls

Experimental treatment arm: TERT mutation-only astrocytoma patients who will receive standard treatment plus TFields therapy at one of 15 participating centers.

- N = 90 patients

- Assumed accrual rate = 2.5 patients/month accumulated over 15 centers
- Accrual period = 36 months
- Follow-up period after the end of accrual = 24 months
- Assumed survival time distribution = Weibull with accelerating hazard and proportional hazards

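### The control cohort's entry lists omit several prognostic criteria that bind the device arm, so the two arms of the primary OS comparison are selected by different rules; the net direction of the resulting bias is uncertain.

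*Combined protocol and SAP*

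**What the plan says.** The device arm is restricted at baseline. Section 5.1 I requires at least 40 Gy of radiotherapy and 80% of the prescribed concurrent TMZ. Section 5.1 K sets the timing: "Adjuvant Temozolomide start date at least 4 weeks, but not more than 6 weeks, from the later of last dose". Section 6.1.2.4 adds the consequence for low counts: "If unable to start within the Cycle 1 start window, the patient will be considered a screen fail". Section 5.2 F sets limits on platelets, neutrophils, grade 4 toxicity, transaminases, bilirubin and GFR. Section 5.2 J excludes "Tumors located in the brain stem and/or the cerebellum".

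The control lists are separate. Section 9.2 begins "In order to be eligible to enroll in the control cohort, an individual must meet all of the following criteria" and gives items A–I. On prior treatment, item G reads "Completed standard chemoradiation and concurrent temozolomide and adjuvant temozolomide", while its sub-item G.a speaks of adjuvant TMZ that was given, or is planned for contemporaneous patients. Section 9.3 gives three exclusions, including "Progressive disease (according to RANO criteria) after temozolomide/RT, at time of starting adjuvant therapy". Section 9.4 bars TTFields.

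The statistical section describes the controls differently. Section 10.1 says historical controls "would have met first tier inclusion/exclusion criteria for the study". Sections 5.1 O and 10.1 describe contemporaneous controls as patients eligible for the trial who decline the device for non-medical reasons. Section 9 itself says only: "Control patients completing chemo/RT after 5/20/2019 will be enrolled as contemporaneous controls".

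The primary analysis in 10.2.1 is a log-rank test. Stratification by MGMT status or extent of resection is optional.

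**The concern.** Without randomisation, shared entry rules are the main protection for the OS comparison, and 9.1 itself treats a homogeneous control cohort as critical. A historical patient who received less than 40 Gy, started adjuvant TMZ late, began it with counts outside the 5.2 F limits, or had a brain stem tumour meets 9.2–9.4 as written but would be turned away from the device arm. If such patients live less long, the control curve falls for reasons unrelated to the device. Stratifying by MGMT or resection would not remove that. The same applies to PFS.

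The undefined 'first tier' wording leaves sites to decide which rules apply to charts whose outcomes may already be known, since section 9 foresees that some historical controls will be deceased.

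**Working it through.** **1. The criteria side by side**

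| Device-arm rule | Where | Counterpart in 9.2–9.4 |
|---|---|---|
| RT at least 40 Gy; 80% of concurrent TMZ | 5.1 I | G requires chemoradiation but no threshold; G.a points back to criteria above it, and none are stated |
| Adjuvant TMZ start at 4–6 weeks | 5.1 K, 6.1.2.4 | None |
| Count and organ-function limits | 5.2 F | None |
| No brain stem or cerebellar tumour | 5.2 J | None |

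Shared by both arms: age, histology and grade, IDH/TERT status, KPS of at least 70, surgery or biopsy, no early RANO progression, no anti-angiogenic agent and no concurrent treatment trial.

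**2. The plan's own power figure**

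Inputs from 10.1 and 10.2: 90 v 90, control median 22 months, Weibull k = 2.0, one-sided alpha 0.05, device accrual 36 months plus 24 months of follow-up (so 24–60 months), control follow-up at most 60 months. I took control follow-up as uniform over 19–60 months, because the historical window is about 41 months and 60 − 41 = 19.

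For a 6-month gain:

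- HR = (22/28)² = 0.617, so |ln HR| = 0.482.
- Expected deaths: control 90 × 0.824 = 74.2; device 67.6.
- Standard error = √(1/74.2 + 1/67.6) = 0.168.
- Power = Φ(0.482/0.168 − 1.645) = Φ(1.22) = 0.889.

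Table 10 gives 0.894. All rows with historical controls only agree within 0.010. The power table is sound, but it assumes that the arms differ only in treatment.

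**3. Effect of the omitted criteria alone**

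Log-rank simulation with the inputs above and no device effect, 4,000 or more trials per case. A share of controls is assumed to fail the device-arm rules and to have a shorter median OS (same k). With matched arms the rejection rate is 0.049, and power for a 6-month gain is 0.893.

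| Assumed median OS of those controls | 10% of controls | 20% of controls |
|---|---|---|
| 18 months | 0.08 | 0.12 |
| 16 months | 0.10 | 0.17 |
| 14 months | 0.11 | 0.22 |
| 11 months | 0.14–0.15 | about 0.31 |

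The documents give neither the share nor the median. Both are assumptions.

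**4. Effect of 9.2 G read literally**

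Device patients need only be candidates for adjuvant TMZ (5.1 J). If controls must have completed it, they must have survived it. Section 6.1.1.1 gives 6 to 12 cycles of 28 days: 6 × 28 = 168 days, about 5.5 months, and 12 × 28 = 336 days, about 11 months. Under the plan's curve, exp(−ln 2 × (t/22)²) is 0.958 at 5.5 months and 0.841 at 11 months, so about 4% or 16% of patients would be removed as early deaths, from the control arm only.

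| Scenario, no device effect | Without G | G = 5.5 months | G = 11 months |
|---|---|---|---|
| No ineligible controls | 0.049 | 0.025 | 0.002 |
| 10% ineligible, median 11 months | 0.14–0.15 | 0.07 | below 0.01 |
| 20% ineligible, median 11 months | about 0.31 | 0.17 | 0.01 |

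With no ineligible controls, G also cuts power for a 6-month gain from 0.893 to 0.83 (5.5 months) or 0.56 (11 months). Depending on how G is read, the net error rate lies above or below 0.05.

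**The case against.** The strongest reply is that the plan intends controls to meet trial criteria, and that its own list contains an offsetting rule. Much of this stands, and it rules out four stronger readings.

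- **That the comparison is tilted toward TTFields.** The omitted items suggest this, but G read literally acts against the device and can outweigh them. G.a's wording conflicts with G, so the documents do not settle which rule applies or the net direction.
- **That a platelet screen failure can become a contemporaneous control.** A reader of 9.2–9.3 alone might infer this. Sections 5.1 O and 10.1 admit only patients who qualify and decline for non-medical reasons. The dates in section 9 separate historical from contemporaneous patients and do not replace eligibility. What remains is that section 9 does not repeat the rule.
- **That the mismatch could never be found at analysis.** Section 9.5 collects a chemoradiation summary and TMZ dates, and 11.2.2.1 requires the screening MRI report and a chemoradiation summary. Dose, timing and site should largely be recoverable. Baseline laboratory values have no listed source.
- **That most baseline restrictions are missing.** The main prognostic ones are shared, and several omitted items (implants, skull defect, bullet fragments) are device-safety rules.

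Item G also acts partly as a proxy for 5.2 F, which is framed around conditions that would prevent adjuvant TMZ. A historical patient who never received it is not eligible. The remaining gap is patients treated despite abnormal values, or after a delay for recovery.

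None of this defines 'first tier' or supplies the missing thresholds for historical controls.

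**Conclusion.** The entry rules differ between arms on criteria with a plausible link to survival, and the planned analysis does not correct for it. The gap mainly concerns the historical controls, expected to be 60 to 80 of 90. It comes from sections 9 and 10 not being reconciled, not from an absence of intent.

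Taken alone, the omissions would raise the one-sided false-positive rate from 0.05 to about 0.08–0.31. That range rests on an assumed 10–20% of controls failing the device-arm rules, with an assumed median OS of 11–18 months. Literal completion of adjuvant TMZ works in the opposite direction and could make the test conservative. The size is therefore only an assumed range and the net direction is open. Two opposing selection rules of unknown strength cannot be relied on to cancel.

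**What to change.** - Apply to controls, as of the start of adjuvant TMZ, the device arm's own chart-verifiable prognostic criteria: 5.1 I, 5.1 K, 5.2 F and 5.2 J. Replace 'first tier' in 10.1 and 10.3 with that list. Device-only safety exclusions need not be copied.
- Reconcile 'completed' in 9.2 G with 'given or planned' in G.a, so that controls, like device patients, qualify on starting adjuvant TMZ and not on finishing it. Tightening the other criteria while leaving G as it stands could bias the comparison against the device.
- State in section 9 that contemporaneous controls are those defined in 5.1 O and 10.1. This bars medical screen failures.
- Add laboratory values at adjuvant start to 9.5. Record tumour location, RT dose, percent of concurrent TMZ and TMZ start date as explicit fields; their sources are largely required already by 9.5 and 11.2.2.1.
- Run the primary comparison in controls who meet these criteria.

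The cost is protocol wording and a few more chart fields. Some controls already identified may become ineligible, so the minimum of 90 may be harder to reach.
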